GSK	Glaxo SmithKline
HRCT	High-resolution computed tomography
ICF	Informed consent Form
ICH	International Conference on Harmonisation
ICS	Inhaled corticosteroid
IMP	Investigational Medicinal Product

ISF	Investigator Site File
ISRCTN	International Standard Randomised Controlled Trials Number
IVRS	Interactive Voice Response System
LABA	Long-acting beta agonist
LAMA	Long-acting muscarinic antagonist
LTOT	Long Term oxygen therapy
MHRA	Medicines and Healthcare products Regulatory Agency
NIMP	Non-Investigational Medicinal Product
PI	Principal Investigator
PIS	Patient Information Sheet
QA	Quality Assurance
REC	Research Ethics Committee
RN	Research Nurse
SAE	Serious Adverse Event
SAR	Serious Adverse Reaction
SDV	Source Data Verification
SPC	Summary of Product Characteristics
SOP	Standard Operating Procedure
SUSAR	Suspected Unexpected Serious Adverse Reaction
TMF	Trial Master File
TMG	Trial Management Group
TSC	Trial Steering Committee

TRIAL SUMMARY

Trial Title	THE MICROBIAL EFFECT OF INHALED STEROIDS IN SEVERE COPD PATIENTS WITH ASSOCIATED BRONCHIECTASIS
Study Acronym	TEMPESTAS
Clinical Phase	Phase 2b
Trial Design	Open Label Randomised Control Trial
Trial Participants	COPD patients with coexistent diagnoses of Bronchiectasis
Planned Number of Participants	80
Planned Number of Sites	3 – 6
Countries Anticipated to be Involved in Trial	UK
Treatment Duration	12 months
Follow up Duration	1 year
Total Planned Trial Duration	30 months
Primary Objective	To investigate the microbiological impact of inhaled corticosteroids over 1 year in patients with GOLD Stage D COPD and a co-diagnosis of bronchiectasis.
Secondary Objectives	Look at the effect of dual vs. triple therapies for all the endpoints mentioned.
Primary Endpoint	Baseline to 1-year change (expressed in log units) in colony forming units per ml between treatment arms (LABA-LAMA plus corticosteroid versus LABA-LAMA only)
Secondary Endpoint	Sputum colour, Sputum microbiota, Sputum bacterial load (>10 ⁶ CFU/ml), Spirometry, Patient symptoms, serum and sputum inflammation, exacerbations and mortality rate.
IMP(s)	Delivered via standard inhalers used routinely in COPD patients: dual bronchodilators (Umeclidinium and Vilanterol 55/22 mcg) vs. triple therapy (Fluticasone furoate, umeclidinium and vilanterol 92/55/22 mcg) both once a day
IMP Route of Administration	Inhaled products
NIMP(s)	Rescue Medication - Salbutamol 5mg/2.5 ml Nebuliser Solution

A key treatment for patients with advanced Chronic Obstructive Pulmonary Disease (COPD) is to optimise the airways using medicines to open the airways.

In patients with recurrent flare-ups, the addition of inhaled corticosteroids to reduce inflammation in the airways is recommended by national and international guidelines.

Recent published studies raised some concern that inhaled corticosteroids can promote chest infections including pneumonia. However, this is controversial, and the risks are uncertain.

We plan to perform a randomised controlled trial involving a high-risk group of severe COPD patients that have recurrent flare-ups due to bronchiectasis (associated widened and damaged airways) in 80 patients from between 3 and 6 NHS hospital sites. This patient group needs special attention as association of bronchiectasis in COPD can make them more prone to these exacerbations and can increase the mortality rate by up to 20-30%.

We aim to assess whether inhaled steroids along with other type of inhalers that open the airways can affect the amount and type of bacteria in the airways. This is a good patient group to test whether inhaled corticosteroids and other inhalers that open up the airways are safe and will improve patient symptoms and improve the burden of bacteria in lungs or not.

40 patients from each group will receive the dual inhaler ANORO ELLIPTA or the triple inhaler TRELEGY ELLIPTA (which includes the inhaled steroid) to determine the effect of the inhaled steroid over a variety of tests including a sputum test, breathing tests, amongst others. We will follow-up all participants for 12 months.

Lay Summary of Trial

1. INTRODUCTION

1.1 BACKGROUND

Chronic Obstructive Pulmonary Disease (COPD) is a major cause of morbidity and mortality internationally. There is increasing recognition that patients with advanced COPD with coexisting bronchiectasis have increased respiratory tract infections and increased mortality¹. Martínez-García et al reported on a series of 91 Spanish patients with well-characterized, clinically stable, moderate to severe COPD2 and found that 58% of these patients had bronchiectasis on CT scanning of the chest. Other recent studies in patients with COPD across all GOLD stages of disease showed bronchiectasis rates of 27% in 75 UK patients. Bronchiectasis was also reported as an associated pathology in 2,164 subjects in the multinational Evaluation of COPD Longitudinally to Identify Predictive Surrogate Endpoints (ECLIPSE) cohort³.

A systematic review and meta-analysis in 2016 have shown that the association with bronchiectasis is an independent risk factor for exacerbation, severity of airway obstruction and mortality in COPD patients⁴. Studies have also shown that association of bronchiectasis on HRCT is common in COPD and is linked with more severe COPD exacerbations, lower airway bacterial colonization, and increased sputum inflammatory markers⁵.

Most guidelines recommend a stepwise approach to inhaler therapy in COPD patients with a long-acting beta 2-agonist (LABA) plus an inhaled corticosteroid (ICS) or a long-acting muscarinic antagonist (LAMA) and LABA combination inhalers, as the first-choice treatment that have a high risk of exacerbations, and then considering escalation to triple therapy with all three class of drugs⁶.

Recently the landmark IMPACT trial showed superiority of triple therapy to both LABA-LAMA and LABA-ICS therapy on the primary endpoint of reduction in the annual rate of on-treatment moderate/severe exacerbations (p<0.001) and a range of other clinically important outcomes, including spirometry and health-related quality of life. This is in keeping with current guidelines of prescribing triple therapy in frequent exacerbators of COPD⁷.

The FLAME trial, on the other hand undertook a randomised, double-blind non-inferiority trial⁸. Patients who had COPD with a history of at least one exacerbation during the previous year were randomly assigned to receive, by inhalation, either the LABA plus the LAMA once daily or the LABA plus the inhaled glucocorticoid fluticasone twice daily. The trial showed that the LABA-LAMA group was more effective in preventing exacerbations than the LABA-ICS group (p <0.001) and was associated with lower incidence of community-acquired pneumonia (p= 0.02). This reaffirms that LABA-LAMA could be a safe alternative if triple therapy is not deemed suitable for some reason in COPD patients with frequent exacerbations.

The main reported risk of ICS in COPD is that of increase risk of pneumonia and hence should be used in accordance to available protocols of COPD management. Despite this data drawn from the Adelphi Respiratory Disease Specific Program, a large multinational (France, Germany, Italy, Spain, UK, USA) cross-sectional survey generating real-world data based on actual clinical practice, showed there is still overuse of inhaled corticosteroids in all groups of disease severity in COPD (33% in Stage A, 38% in Stage B, 54% in Stage C and 51% in Stage D) 9 . Even in bronchiectasis patients, the UK National Audits 2010 (n=1460) and 2011 (n=2404) revealed that ICS are used in 78–81% with a mean dose of 1094–1252 μ g/day 10 , despite BTS National Guidelines recommending not for routine use.

Recent study by Contoli et al assessing the effect of LABA-ICS vs. just a LABA on bacterial and viral loads in patients with moderate COPD showed an increase in bacterial load for

patients treated with ICS. However post hoc analysis indicated that this change was driven in patients with eosinophil counts of $\leq 2\%$ in peripheral blood¹¹.

This study therefore has selected this subgroup of severe COPD (GOLD 2017 classification Stage D) with a co-diagnosis of bronchiectasis as a cohort with the highest risk of infection. The aim is to explore the impact of inhaled corticosteroids in this high-risk group. No similar study has been conducted to date from a PubMed search on the 17th of September 2020.

1.2 RATIONALE FOR STUDY

Inhaled corticosteroids are routinely prescribed for patients with advanced COPD with recurrent exacerbations by international guidelines but their deleterious effect regarding risk of infection and pneumonia remain controversial and uncertain.

This is a proof-of-concept study to assess the effects of inhaled corticosteroid therapy in patients with severe Chronic Obstructive Pulmonary Disease (COPD), Global Initiative for Chronic Obstructive Lung Disease (GOLD) stage D and a co-diagnosis of bronchiectasis and compare it with other classes of inhalers.

The trial essentially wants to review the judiciousness of inhaled corticosteroids (ICS) in this group of COPD patients with coexistent bronchiectasis. One of the known side effects of ICS is risk of pneumonia and hence is all the more important to address and answer this question in this cohort of patents. We will however be closely monitoring these patients with the symptom diaries, good worsening advice and follow up as necessary. The FLAME trial as mentioned in the protocol also showed superiority of dual bronchodilator over triple therapy, so we are reassured those patients will manage to keep their symptom burden under control (if they are in the dual bronchodilator arm of the study) with careful monitoring as planned by the research team.

2. STUDY OBJECTIVES

2.1 OBJECTIVES

2.1.1 Primary Objective

In patients with severe COPD and bronchiectasis, does the addition of inhaled corticosteroids:

- Alter the microbial load of pathogens?
 - o ICS beneficial effect would lead to an expected reduction in microbial load, with less significant bacterial loads (10 colony forming units/ml or more).
 - o ICS detrimental effect, would lead to an expected increased microbial load, with significant bacterial loads (10 colony forming units/ml or more)¹².

This would be assessed between the two groups (LABA-LAMA-ICS and LABA-LAMA arms).

2.1.2 Secondary Objectives (between two arms of the study) to assess if ICS:

- 1. Are beneficial, patients will have a broadened microbial diversity in sputum microbiata and if detrimental there would be loss of this diversity¹³⁻¹⁵.
- 2. Alter sputum colour, airways and systemic inflammation. The mechanism of inhaled corticosteroids is anti-inflammatory, and the hypothesis is that inhaled

corticosteroids might improve sputum colour and reduce sputum and serum inflammation¹².

- 3. Impact on microbial and mycobial community composition as explained in endpoints section 2.
- 4. Impact on spirometry (forced expired volume in 1 second, forced vital capacity, its ratio and mid expiratory flows FEF25-75).
- 5. Impact on health status using well-validated quality of life questionnaires in bronchiectasis (COPD Assessment Tool¹⁶ and St George's Respiratory Questionnaire¹⁷).
- 6. Moderate/ severe exacerbation rate and time to first moderate/ severe exacerbation.
- 7. Investigate if addition of inhaled corticosteroid has an overall beneficial/detrimental effect to the mortality rate and whether that correlates with the microbial diversity that we are also assessing in these 2 groups.

2.2 ENDPOINTS

2.2.1 Primary Endpoint

A Baseline to 1-year change (expressed in log units) in colony forming units per ml between treatment arms (LABA-LAMA plus corticosteroid versus LABA-LAMA only) 11-12

2.2.2 Secondary Endpoints

- 1. Change in sputum microbial diversity and microbial biomass (see analyses below for details) ¹³⁻¹⁵ between the two arms.
- 2. **Sputum colour** as assessed by a standardised colour chart- patients are graded as mucoid (clear or grey phlegm, muco-purulent (light yellow or green) and purulent (dark yellow or green) ¹⁸.
- 3. **a) Microbial community composition** (gram negative/positive ratio, abundance of potential pathogens etc.)¹⁴
 - **b) Fungal microbiome**: between the two groups to see if ICS can influence the heterogeneity of the fungal community in terms of absolute and relative abundance.²⁰⁻²¹
- 4. **Spirometry**: forced expired volume in 1 second, forced vital capacity and its ratio and mid expiratory flows (FEF25-75) (attenuation of decline in lung function would be of long-term benefit to patients if found).
- 5. **Quality of Life**: quality of life assessed by the COPD Assessment Tool (CAT) ¹⁶ and St. George's Respiratory Questionnaire¹⁷. Breathlessness is included as part of this questionnaire.
- 6. **Sputum inflammation**: we will assess sputum myeloperoxidase as a measure of neutrophil burden and free elastase activity¹².
- 7. **Serum inflammation**: we will measure white cell count and differential, C Reactive Protein (CRP) and intercellular adhesion molecule 1 (ICAM-1)¹¹ Previous research has shown that at high bacterial loads there is increased ICAM-1¹²
- 8. **Exacerbations**: These would be categorised as
 - *time to the *first moderate or severe exacerbation* requiring treatment with antibiotics and/steroids, **number of exacerbations* (needing antibiotics and/steroids) over 12 months including hospitalisations

*number of participants with radiologically confirmed *pneumonia* over this period.

- 9. **Mortality rate** between the 2 arms of the study groups. Considering the group's overall but also separately broken down by microbe and microbial diversity.
- 10. Safety endpoints: The incidence of all AE and SAE across both treatment arms would be described as well as a safety endpoint. To assess and investigate safety and benefits of a trial design like this, we will also document parameters such as respiratory failure), hospitalised exacerbations (along with other exacerbation data as specified above), and trial dropout due to worsening COPD symptoms as safety endpoints. This would be documented between both the arms of the study.

[figure not shown]
3. STUDY DESIGN

TEMPESTAS is a multi-centred, open label, parallel group randomised study across between 3 - 6 sites. We plan to recruit 80 patients.

To optimise the airflow limitation, we are treating all patients with a combined LAMA and LABA for a washout period of 4 weeks ANORO ELLIPTA 1 puff once daily (combination of umeclidinium 55mcg and vilanterol 22mcg once a day) and the study drugs selected are first line on all our formulary.

These patients will then be randomised in a 1:1 ratio to LABA-LAMA or LABA-LAMA plus additional inhaled corticosteroids (Trelegy Ellipta 92/55/22 I puff once a day). All treatment durations then would last for a year.

3.1 Trial Flow

3.2 Stopping criteria

The IMPs used in the study are routine treatments for the cohort. Safety endpoints will be reviewed by the DMC throughout the study and will determine if there is reason to stop the trial on safety grounds. Any interim decision to stop the IMP on any particular participant would be a clinical decision taken by the PI or the CI.

3.3 NUMBER OF PARTICIPANTS

We aim to recruit 80 patients with moderate-severe COPD with coexistent diagnoses of radiological proven bronchiectasis. Patients will be followed up for 12 months after randomisation.

3.4 INCLUSION CRITERIA

Subjects eligible for enrolment in the study must meet all of the following criteria:

- 1. **Informed Consent:** A signed and dated written informed consent prior to study participation.
- 2. Type of subject: Outpatient.
- 3. Age: Subjects 40 years of age or older at screening visit
- 4. Gender: Male or female subjects
- 5. **COPD Diagnosis:** An established clinical history of COPD as documented in medical notes in accordance with the definition by the American Thoracic Society/European Respiratory Society.

COPD-Bronchiectasis definition:

We will include patients with:

COPD-Bronchiectasis coexistence: smoking history of greater than 10 pack year, with a post bronchodilator FEV1/FVC ratio <0.7 with coexistent bronchiectasis on a high-resolution CT Chest (increased broncho-arterial ratio in two or more lobes of the lung). CT scans would have been done prior to recruitment as a part of usual clinical pathway.

- Two or more exacerbations in the last 1-year (requiring antibiotics and/steroids) or one or more hospitalisation in accordance with GOLD D (2017) classification (high risk more symptom COPD patients) but clinically stable during screening period.
- Clinically stable is defined as not requiring antibiotics and or steroid 4 weeks prior to study entry. This will be checked during the randomisation visit from patient history and documented by the research nurses.
- 6. **Smoking History:** Current or former cigarette smokers (cigarettes or rolled tobacco) with a history of cigarette smoking of >10 pack-years at screening (visit 1) [number of pack years = (number of cigarettes per day / 20) x number of years smoked (e.g., 20 cigarettes per day for 10 years, or 10 cigarettes per day for 20 years)]. Previous smokers are defined as those who have stopped smoking for at least 6 months prior to Visit 1. Note: Pipe and/or cigar use cannot be used to calculate pack-year history.

3.5 EXCLUSION CRITERIA

Subjects meeting any of the following criteria **must not** be enrolled in the study:

1. **Pregnancy**: Women who are pregnant or breast feeding or are planning on becoming pregnant during the study.

- 2. **Asthma:** Subjects with a current/ concurrent primary diagnosis of asthma.
- 3. α 1-antitrypsin deficiency: Subjects with known α 1-antitrypsin deficiency as the underlying cause of COPD.
- 4. **Other respiratory disorders**: Subjects with active tuberculosis, active lung cancer, primary diagnosis of sarcoidosis, primary diagnosis of lung fibrosis, primary pulmonary hypertension, or other interstitial lung diseases (ILD) as primary respiratory condition. Subjects diagnosed with mild ILD may be included in the trial, as long as ILD is not the predominant respiratory condition.
- 5. **Lung resection**: Subjects with lung volume reduction surgery within the 12 months prior to Screening.
- 6. **Risk Factors for Pneumonia**: immune suppression (e.g., HIV, Lupus) or other risk factors for pneumonia, when patients are on long standing immunosuppressive drugs or have neuromuscular conditions affecting control of the upper airway, such as Parkinson's disease. Motor Neuron Disease or Myasthenia Gravis.
- 7. Pneumonia and/or moderate or severe COPD exacerbation that has not resolved at least 30 days prior to Screening and at least 30 days following the last dose of oral/systemic corticosteroids (if applicable). In addition, any subject that experiences pneumonia and/or moderate or severe COPD exacerbation during the washout period will be excluded.
- 8. Other Respiratory tract infections that have not resolved at least 7 days prior to screening including COVID19 infections (would be assessed and decided by the PI corroborated by patient history and medical notes if deemed necessary).
- 9. **Other diseases/abnormalities:** Subjects with historical or current evidence of any of the following clinically significant abnormalities that are uncontrolled:
 - cardiovascular
 - neurological
 - psychiatric (including documented psychiatric reactions or hypersensitivity to oral steroids)
 - renal
 - hepatic
 - immunological
 - gastrointestinal
 - urogenital (e.g., significant prostatic hyperplasia in men or bladder outflow obstruction that precludes use of a LAMA)
 - nervous system
 - musculoskeletal (including known significant osteoporosis)
 - skin
 - sensory
 - endocrine (including uncontrolled Type 1 or 2 diabetes or thyroid disease)
 - ocular (e.g., significant narrow angle glaucoma that precludes patients from getting a LAMA)
 - haematological

Significant is defined as any disease that, in the opinion of the Investigator, would put the safety of the subject at risk through participation, or which would affect the efficacy or safety analysis if the disease/condition exacerbated during the study.

- 10. **Unstable liver disease** as defined by the presence of ascites, encephalopathy, coagulopathy, oesophageal or gastric varices or persistent jaundice.
- 11. **Unstable or life-threatening cardiac disease**: subjects with any of the following at Screening (Visit 1) would be excluded:
 - *Type 1 Myocardial infarction or unstable angina in the last 6 months
 - *Type 2 Myocardial infarction (more common in severe COPD patients) in last 3 months.

- *Unstable or life-threatening cardiac arrhythmia requiring intervention in the last 3 months
- * NYHA Class IV Heart failure
- 12. Abnormal and clinically significant 12-Lead ECG finding: The PI will determine the clinical significance of each abnormal ECG finding in relation to the subject's medical history and exclude subjects who would be at undue risk by participating in the trial.

An abnormal and clinically significant finding that would preclude a subject from entering the trial is defined as a 12-lead tracing that is interpreted as, but not limited to, any of the following:

*AF with rapid ventricular rate >120 BPM;

*sustained or non-sustained VT;

- *Second degree heart block Mobitz type II and third-degree heart block (unless pacemaker or defibrillator had been inserted)
- * QTcF ≥500 msec in patients with QRS <120 msec and QTcF ≥530 msec in patients with QRS ≥ 120 msec
- 13. **Other Contraindications**: A history of allergy or hypersensitivity to any oral steroid or corticosteroid, anticholinergic/muscarinic receptor antagonist, beta2-agonist, lactose/milk protein or magnesium stearate or a medical condition such as narrowangle glaucoma, uncontrolled symptomatic prostatic hypertrophy or bladder neck obstruction that, in the opinion of the Investigator contraindicates study participation.
- 14. Cancer: Subjects with carcinoma that has not been in complete remission for at least 5 years. Subjects who have had carcinoma in situ of the cervix, prostrate carcinoma, squamous cell carcinoma and basal cell carcinoma of the skin would not be excluded based on the 5year waiting period if the subject has been considered cured by treatment.
- 15. **Oxygen therapy**: Use of long-term oxygen therapy (LTOT) described as resting oxygen therapy >3L/min (Oxygen use up to 3L/min flow is not exclusionary.)
- 16. **Medication prior to spirometry**: Subjects who are medically unable to withhold their salbutamol for the 4-hour period required prior to spirometry testing at each study visit. This will be gathered from the patient history during the study visit.
- 17. **Pulmonary rehabilitation**: Subjects who have participated in the acute phase of a Pulmonary Rehabilitation Program within 2 weeks prior to Screening or subjects who plan to enter the acute phase of a Pulmonary Rehabilitation Program during the study. Subjects who are in the maintenance phase of a Pulmonary Rehabilitation Program are not excluded.
- 18. **Drug/alcohol abuse**: Subjects with a documented known or suspected history of alcohol or drug abuse within the last 1 year.
- 19. **Non-compliance**: Subjects at risk of non-compliance, or unable to comply with the study procedures. Any infirmity, disability, or geographic location that would limit compliance for scheduled visits. Non-compliance with requirement for adherence to at least 50% compliance with washout medication, verified at visit 2. Non-compliance with requirement for adherence to at least 50% compliance with trial medication, verified at visit 5.
- 20. **Inability to read or write English**: In the opinion of the Investigator, any subject who is unable to read or write and/or would not be able to complete study related materials in English.
- 21. **Medication prior to screening**: Use of the following medications within the following time intervals prior to Screening (Visit 1) or during the study:

Systemic, Oral, parenteral Corticosteroids	30 days (Except during the study oral/systemic corticosteroids may be used to treat COPD exacerbations/pneumonia. Intraarticular injections are allowed.
Any other investigational drug	30 days

- 22. **Suspected atypical infection** like Tuberculosis or fungal infections.
- 23. Already enrolled in any other clinical trial of an Investigational Medicinal Product or device.

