4.4 PARTICIPANT COMPLIANCE

Study drug compliance will be assessed and recorded by trial personnel at the randomisation, six month and twelve-month (end of study) visits. The Investigator or delegate will collect used and unused medication and packaging from the patient.

Study drug compliance will be assessed by checking the dose indicator on the inhalers. Adherence to COPD treatment in this patient population overall is good. However, if a patient failed to meet a minimum 50% compliance with study medication during the washout period (i.e., they did not take the medication for at least 14/28 days with no exceptional circumstances to justify this), they will not be eligible to continue to be randomised. A 50% threshold for compliance will apply for compliance for the duration of the study.

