6.4 Visit 5 – 12 months/Final Assessment

A final Assessment Visit will be completed for all participants at completion of the study or earlier if required.

The following assessments are expected to be conducted in clinic and must be recorded in the CRF:

- Adverse Events
- Any exacerbations of COPD
- Any changes in concomitant medications
- Pregnancy and contraceptive review (if there is concern of pregnancy, another pregnancy test will be administered)
- Vital signs
- Blood analysis (Biochemistry)
- Sputum collection
- ECG
- ICAM-1 collection
- Adherence to study treatment
- Spirometry
- SGRQ-C assessments
- COPD Assessment Tool (CAT)
- Modified MRC breathless score

- Return of unused study medication and accountability
- Study medication adherence and accountability

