3.1 Analysis populations

Participants will be included in the analysis in the groups to which they were originally assigned irrespective of treatment actually received with the exception of adverse event data which will also be presented by treatment received.

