4.2 Attendance/Compliance

For each visit the number and percent of participants will be presented and broken down by treatment.

Study drug compliance will be assessed and recorded by trial personnel by checking the dose indicators on the medication returned at the one month, six month and twelve-month (end of study).

Absolute compliance is calculated as: number of doses dispensed - number of doses returned

Percentage compliance is calculated as:

$$\frac{(number\ of\ doses\ dispensed-number\ of\ doses\ returned)}{(final\ visit\ date\#-dispensing\ visit\ date)}*100$$

where a person has terminated the trial early, the timeframe over which the drugs should have been taken will be determined up to the point at which they withdrew from the trial so the change of status date will be used in place of the final visit date.

A 50% threshold for compliance will apply for the duration of the study.

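### An enrolment exclusion is judged at the final visit, the 50% on-treatment threshold has no stated use, and the SAP compliance formula counts unreturned inhalers as fully taken

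*Protocol*

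**What the plan says.** Protocol 3.5 introduces its list with "Subjects meeting any of the following criteria must not be enrolled in the study". Item 19 of that list holds two compliance clauses:

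- Washout: "Non-compliance with requirement for adherence to at least 50% compliance with washout medication, verified at visit 2". Visit 2 is the randomisation visit, and Protocol 4.4 gives the consequence: the patient is not randomised.
- Trial medication: "Non-compliance with requirement for adherence to at least 50% compliance with trial medication, verified at visit 5". Protocol 6.4 describes visit 5 thus: "A final Assessment Visit will be completed for all participants at completion of the study or earlier if required".

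For the treatment period, Protocol 4.4 says only "A 50% threshold for compliance will apply for compliance for the duration of the study". SAP 4.2 repeats this almost word for word. Neither says what follows when a participant is below 50%.

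SAP 3.1 sets the analysis population: "Participants will be included in the analysis in the groups to which they were originally assigned irrespective of treatment actually received". Its one exception is that adverse events are also shown by treatment received. No per-protocol set is defined.

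On measurement, SAP 4.2 states: "Absolute compliance is calculated as: number of doses dispensed - number of doses returned". The percentage divides this by the days from dispensing to the final visit, or to the change-of-status date after early termination. The count comes from "checking the dose indicators on the medication returned at the one month", six-month and twelve-month visits. Protocol 4.1.6 asks for returns at the end of washout, at 6 months, and at 12 months or discontinuation. Protocol 4.4 assesses compliance at randomisation, six and twelve months. Neither schedules a one-month return.

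**The concern.** A criterion in an enrolment list has to be decidable at enrolment. This one depends on behaviour during the following year, in an open-label trial where adherence may respond to knowing the allocation. The reader cannot tell whether it does anything. Left open, it invites a choice about low compliers after the data are in.

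The formula is a separate matter. A dose that was not handed back is not necessarily a dose taken. Participants who leave early or lose inhalers are those whose adherence is least certain, and the formula gives them the highest scores. If the 50% figure is ever used, even descriptively, it will be passed too easily.

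**Working it through.** **1. The clauses side by side**

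| Clause | When decided | Can it bar enrolment or randomisation? | Stated consequence |
|---|---|---|---|
| Washout, under 50% | Visit 2 | Yes | Not randomised (Protocol 4.4) |
| Trial medication, under 50% | Visit 5 | No; the participant is randomised and treated | None |

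At visit 5 an exclusion could act only on data already collected, and SAP 3.1 does not allow that. Either the clause conflicts with SAP 3.1, or it is inert and the threshold has no use.

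**2. What the formula measures**

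Inputs:
- 30 doses per inhaler (Protocol 4.1.1).
- Seven inhalers at randomisation and a further six months' supply at month 6 (Protocol 4.1.7). Assuming one inhaler per month for the second supply, that is 7 + 6 = 13 inhalers, or 390 doses.
- Month-12 window of 3 weeks either side (Table 1), so 344 to 386 days around 365.
- The formula is applied over the whole treatment period.

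Doses dispensed minus doses returned equals doses used from returned inhalers plus 30 for every inhaler not returned. The SAP figure is therefore the upper bound of true use. It is right only if every missing inhaler was emptied by use.

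Results over 365 days:
- One untouched inhaler not returned: 30/365 = 8.2 percentage points (30/386 = 7.8 to 30/344 = 8.7).
- True use of 40% is 146 doses, leaving 390 - 146 = 244. If all come back, the score is (390 - 244)/365 = 40.0%. With two untouched inhalers missing, 244 - 60 = 184 come back and the score is (390 - 184)/365 = 206/365 = 56.4%, a pass.
- The same participant with one missing: 176/365 = 48.2%, still below 50%.
- Nothing returned for a full year: 390/365 = 106.8% (390/386 = 101.0% to 390/344 = 113.4%), whatever was taken.
- Withdrawal at day 90 with nothing returned: 210/90 = 233%.

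A lost inhaler may also be replaced (Protocol 4.1.7), which raises the dispensed count further.

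**3. Sample size, for context**

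Protocol 8.1 gives a difference of 0.76, SD 0.98, two-sided 5% and 90% power. The standardised difference is 0.76/0.98 = 0.776. The exact two-sample t calculation gives 35.93, so 36 per arm, with 90.1% power. Allowing 10% dropout, 36/0.9 = 40 per arm. The plan's figure reproduces.

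The documents give no rate of compliance below 50%. If a fraction of the 36 were removed (an assumption):

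| Removed | Per arm | Power |
|---|---|---|
| 0% | 36 | 90.1% |
| 5% | 34.2 | 88.5% |
| 10% | 32.4 | 86.7% |
| 20% | 28.8 | 82.4% |

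**The case against.** A reader might infer that participants below 50% will be removed and the randomised comparison broken. The documents do not support that. The list in Protocol 3.5 governs enrolment, the withdrawal reasons in Protocol 3.12.3 do not include non-compliance with medication, and SAP 3.1, in the later document (27 June 2025 against 2 May 2024), keeps everyone as assigned. For the same reason the power losses above are hypothetical and do not follow from the plan. Protocol 4.4 also expects adherence in this population to be good.

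The formula has no inferential role: no analysis set, outcome or sensitivity analysis uses it. Nor does the SAP abandon the dose indicator. It reads the indicator on returned inhalers, so the gap is confined to those that do not come back.

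The larger scores need unusual circumstances. Returns are requested at discontinuation and a final visit is offered. The first clinic visit after randomisation is at month 6, and someone lost around then, at about day 183, with nothing returned scores 210/183 = 115%. A score of 233% is visibly impossible and would be queried. The pharmacy manual cited in Protocol 4.1.6 is not available and might contain a rule for missing inhalers.

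It would also go too far to say that the one-month contact can only be a telephone call. Table 1 and Protocol 6.6 present it that way, but Protocol 5.2 allows a site visit and lists compliance among the checks.

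All of this limits the consequence. It does not make the visit-5 clause workable, give the threshold a use, or supply the SAP's missing rule. The 56.4% case matters more than the impossible scores because it looks plausible and passes.

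**Conclusion.** Two wording defects stand. First, an enrolment criterion cannot be applied when enrolment is decided. It either conflicts with SAP 3.1 or does nothing, and in the second case the 50% on-treatment threshold has no stated use. Second, the SAP formula can only overstate compliance when inhalers are missing, by up to 8.2 points per inhaler over a year, which is enough to move a 40% user with two missing above the threshold. These figures assume 13 inhalers over 365 days and untouched missing inhalers; an inhaler emptied by use and then discarded causes no error.

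The bias affects the compliance summary and any later use of the 50% figure. The as-randomised primary comparison and the sample size of 80 are unaffected. The one-month return in SAP 4.2 is a further mismatch to reconcile.

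**What to change.** - **Protocol 3.5 item 19:** reconcile with SAP 3.1 by taking the visit-5 clause out of the enrolment criteria. The washout clause stays.
- **Protocol 4.4 and SAP 3.1 and 4.2:** state that no randomised participant is removed from the as-randomised analysis for compliance, and that the 50% on-treatment threshold is descriptive. A supplementary analysis set is optional and not needed to resolve this point.
- **SAP 4.2:** compute doses taken as the sum, over returned inhalers, of 30 minus the dose-indicator reading. Report the number of unreturned inhalers by arm as unknown, and give each affected participant a range with 0 and 30 doses per missing inhaler. In the example above the range is 146/365 = 40.0% to 206/365 = 56.4%. Show participants whose range spans 50% as undetermined.
- **One-month return:** reconcile SAP 4.2 with Protocol 4.1.6, 4.4 and 5.2 and Table 1.

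The cost is wording in both documents and a little more analysis work. Some participants will have a range instead of a single figure. Dose indicators are already checked under Protocol 4.4. The team should confirm that the number of inhalers returned is recorded alongside the doses remaining, since the calculation needs both.
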